9.8.15. Study Drug Dispensation and Collection

Study drug will be dispensed to the subject and collected from the subject as indicated in [Table 3](#). The dispensing schedule will be subject to availability. Dispensed treatment kits from each visit should be returned to the site for collection at the subsequent visit.

9.8.16. Adverse Event Collection

Subjects will be observed for general appearance, presence of illness or injury, or signs indicative of a concurrent illness as indicated in [Table 3](#). Subjects must be instructed to volunteer any information regarding AEs on or after the first dose of study drug or query the subjects with an open question regarding any AEs they may be experiencing (*e.g.*, “How have you been feeling since your last visit?”). Any findings are to be documented. Subjects must be asked if they have been hospitalized, had any accidents, used any new medications, or changed concomitant medication regimens (including prescription drugs, over-the-counter medications, vitamins, herbal products, and minerals). Responses must be documented in the source documents.

9.8.17. Optional Viral Serology Study

Infection with SARS-COVID-2 may range from asymptomatic to disease requiring hospitalization. Given a high number of asymptomatic or minimally symptomatic infections, it is possible that a proportion of the population could have been exposed and recovered, especially in the weeks before active testing and surveillance became available in the United States. Moreover, healthcare workers who work in the “frontline” or directly with patients infected with SARS-COVID-2, are at higher risk of infection.

Another important aspect of finding detectable IgG antibody titers is the use of plasma from recovered patients with COVID-19 in a similar fashion as it has previously been used to treat outbreaks other potentially lethal infectious diseases such as SARS, Ebola, diphtheria, measles, etc. before a vaccine was available. On March 24, 2020, the FDA announced a pathway to facilitate access to COVID-19 convalescent plasma for use in patients with serious or immediately life-threatening COVID-19 infections. This therapy relies on circulating serum antibodies that are able to, either prevent infection via blocking interaction of the virus with the host cell receptor, or that can potentiate antibody-dependent cell-mediated cytotoxicity (ADCC).

Hypothesis: A proportion of healthcare workers have previously been exposed and recovered from SARS-COVID-2. Detectable IgG antibodies against SARS-COVID-2 would indicate evidence of past infection. Moreover, the development of IgM or IgG antibodies during the study period would indicate exposure to the virus.

Inclusion criteria:

- All healthcare workers participating in the chemoprophylaxis trial will be offered participation.

Accordingly, the Biotechnology Center within the Baylor Institute for Immunology Research has initiated a viral serology study to collect serum/plasma samples from those participating in the study that also agree to have blood samples obtained. The donors that have the highest titers of

antibodies directed to SARS-COV-2 proteins will have the highest potential for eliciting potent therapeutic benefit.

Individuals who agree to participate in the viral serology sub-study will be required to sign a separate ICF before collection of the samples. Subjects are not required to participate in the viral serology sub-study in order to enroll in the primary study. Samples for viral serology sub-study should be collected on day 1/baseline (pre-dose) and on days 14, 28 and 42 as indicated in [Table 3](#).

Healthcare worker blood sampling: Initial blood sampling for plasma collection will be planned via staff at the BSWRI BPM core laboratory, which is classified as a Bio Safety Level 2 lab (BSL-2). The Core will manage documentation, storage, and appropriate dispersal of the collected materials.

Serology testing: Samples will be processed by the BPM Core staff for viral inactivation. Serology at the Biotechnology Center will be undertaken with read out of SARS-COV-2-specific plasm pan-Ig and/or or IgG. If needed for throughput, samples can be pooled and assayed to identify positive pools, followed by deconvolution.

Biotechnology Center will run serology tests using either solid phase ELISA or bead-based Luminex™ multiplexed assay (the latter is ~10-fold more sensitive). Recombinant protein components of SARS-COV-2 are the basis of these assays, and these will either be purchase commercially (Sinobiologicals) or made in house. If commercial assay kits become available, then they will be used for testing or validation of in-house assays.

Serology study Endpoints:

- The primary endpoint is to determine the proportion of healthcare workers that have detectable SARS-COVID-2 IgG at baseline
- Secondary endpoint: determine the proportion of healthcare workers who seroconvert as evidenced by detectable IgM and/or IgG levels throughout the study.

Considerations/Interventions:

- All serum samples will be paired with a Nasopharyngeal swab PCR as this is performed weekly.
- Participants with detectable IgM and no detectable IgG against SARS-COVID-2 will be considered recently infected and will require further evaluation by Employee health.
- Participants who have only detectable IgG will be considered previously exposed and with resolved infection.
- Participants with detectable IgG and IgM will be considered to have been infected and on recovery phase.

Study termination:

- Participants may elect to stop participation at any time.

Management of COVID-19 positive cases:

- Those who become infected during the trial will be encouraged to do the serology testing two weeks after they become positive, if feasible.

Management of missed visits:

Subjects who miss the Day 42 serology for any reason (subject availability, had to leave before completing visit, etc.) will be reminded during the Day 49 visit that they did not have their final serology draw done at Day 42. They will be asked if they wish to have the final draw done at the final visit (“today”). This will allow them to receive at least the “before and after” results of their antibodies during the study (all subjects consented to Day 1 serology draws and had at least 1 sample collected) in addition to any samples they consented to have collected during the study, and they will be informed that this helps the researcher gather more data on the prevalence of antibodies in healthcare workers at high risk of COVID-19 infection.

In all cases, this conversation will be documented on the Day 49 source documents, including that it was not done at Day 42 and why, and that the subject is agreeing or refusing to have it drawn at Day 49. For subjects that did have some procedures at Day 42 but were not able to complete the serology sample collection, this is additionally documented in the Day 42 source documents. For subjects who missed Day 42 entirely, there will be a notation in the subject file that the visit was missed.

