Based on more than 500 genetic sequences submitted to GISAID (the Global Initiative on Sharing All Influenza Data), the virus has not drifted to significant strain difference and changes in sequence are minimal. There is no evidence to link sequence information with transmissibility or virulence of severe acute respiratory syndrome coronavirus 2 (SARS-CoV-2), the virus that causes COVID-19.

SARS-CoV-2, like other emerging high-threat pathogens, has infected health-care workers in China and several other countries. To date, however, in China, where infection prevention and control was taken seriously, nosocomial transmission has not been a major amplifier of transmission in this epidemic. Epidemiological records in China suggest that up to 85% of human-to-human transmission has occurred in family clusters and that 2055 health-care workers have become infected, demonstrating that patient to healthcare worker is tractable. However, there have been no major nosocomial outbreaks and some supporting evidence that some health-care workers may have acquired infection or transmitted the infection to their families. These findings suggest that close and unprotected exposure is required for transmission by direct contact or by contact with fomites in the immediate environment of those with infection. Continuing reports from outside China suggest the same means of transmission to close contacts

and persons who attended the same social events or were in circumscribed areas such as office spaces or cruise ships. It has been suggested that a healthcare worker that had 15-30 min of exposure within 6 feet of an infected patient without PEP could acquire the infection.

Intensified case finding and contact tracing are considered crucial by most countries and are being undertaken to attempt to locate cases and to stop onward transmission. Confirmation of infection at present consists of PCR for acute infection, and although many serological tests to identify convalescent antibodies which confer potential immunity are being developed they require validation with well characterized sera before they are reliable for general use.

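### The serology sub-study reports the crude proportion with detectable IgG as past infection, uncorrected for assay error: biased upward at low prevalence, downward above a break-even value

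*Protocol*

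**What the plan says.** The sub-study's hypothesis, in Protocol 9.8.17, is that "A proportion of healthcare workers have previously been exposed and recovered from SARS-COVID-2". The evidence for it is given in the next sentence: "Detectable IgG antibodies against SARS-COVID-2 would indicate evidence of past infection". The endpoint follows directly: "The primary endpoint is to determine the proportion of healthcare workers that have detectable SARS-COVID-2 IgG at baseline". The same reading is applied to individuals: "Participants who have only detectable IgG will be considered previously exposed and with resolved infection". The secondary endpoint is to "determine the proportion of healthcare workers who seroconvert as evidenced by detectable IgM and/or IgG levels throughout the study", with draws at baseline and Days 14, 28 and 42.

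The assay is left open between an ELISA and a bead-based Luminex method, with purchased or in-house antigen. The only performance statement is that the second is about ten times more sensitive. On validation, 9.8.17 says only: "If commercial assay kits become available, then they will be used for testing or validation of in-house assays". The Introduction (section 5) says of serological tests in general that "they require validation with well characterized sera before they are reliable for general use".

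No cut-off, sensitivity, specificity, confirmatory test, interval or correction is stated. The SAP has no section on serology.

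**The concern.** The proportion above a detection limit mixes true past infections with false positives and leaves out past infections that the assay misses. It equals the prevalence of past infection only if the assay is perfect or if the two errors happen to cancel. When few workers have been infected, false positives can make up most of the count. When many have been infected, missed cases dominate and the figure is too low.

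Two things are at stake. The sub-study's headline number may be wrong in either direction by an amount nobody can judge, because the figures needed to judge it are not required to be recorded. And frontline workers, who according to the missed-visits paragraph of 9.8.17 receive their antibody results, may be told that they have had and cleared an infection when the reading was an assay error.

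**Working it through.** There is no figure in the plan to reproduce: the sub-study states no sample size, precision or expected prevalence.

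**Inputs from the documents**
- Number tested: at most 360 (Protocol 7.2; 9.8.17 offers serology to all participants). The Synopsis excepts registry controls from blood testing. If that covers serology too, the maximum is 180. Uptake is optional and unstated.
- Draws after baseline: three (Table 3 and 9.8.17).

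**Assumptions, not in the documents**
- Specificity (Sp) 98% to 99.9%; sensitivity (Se) 90%, with 80% and 100% as a range; true prevalence (p) 1% or 2%.

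**Step 1: bias of the crude proportion**

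Crude = p × Se + (1 − p) × (1 − Sp). False share = (1 − p)(1 − Sp) / crude. The crude figure equals the truth at the break-even p* = (1 − Sp) / [(1 − Sp) + (1 − Se)]. Below p* it overstates and above p* it understates.

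For Sp 99%, Se 90% and p = 1%: crude = 0.009 + 0.99 × 0.01 = 0.0189; false share = 0.0099 / 0.0189 = 52%; p* = 0.01 / 0.11 = 9.1%.

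| Sp | Crude at p = 1%, Se 90% | False share | Break-even p*, Se 90% |
|---|---|---|---|
| 98% | 2.9% | 69% | 17% |
| 99% | 1.9% | 52% | 9% |
| 99.5% | 1.4% | 35% | 4.8% |
| 99.9% | 1.0% | 10% | 1.0% |

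Sensitivity hardly alters the low-prevalence result. At Sp 98% and p = 1%, the crude figure is 0.008 + 0.0198 = 2.8% with Se 80%, and 0.010 + 0.0198 = 3.0% with Se 100%. It does move the break-even. At Sp 98%, p* is 0.02 / 0.22 = 9.1% with Se 80%; with Se 100% the crude figure never understates.

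**Step 2: positives when nobody has been infected**

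P(at least one positive) = 1 − Sp^n. For n = 180 and Sp 99%: 1 − 0.99^180 = 84%.

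| Sp | n = 180 | n = 360 |
|---|---|---|
| 98% | 97% | 99.9% |
| 99% | 84% | 97% |
| 99.5% | 59% | 84% |
| 99.9% | 16% | 30% |

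**Step 3: seroconversion**

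If assay errors at the three later draws were independent, an uninfected worker would have at least one false IgG reading with probability 1 − 0.98³ = 5.9% at Sp 98%, or 1 − 0.99³ = 3.0% at Sp 99%. A worker whose false reading is stable over time would already be reactive at Day 1, and would not be counted if conversion is defined against Day 1.

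**Step 4: what correction can deliver**

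Rogan-Gladen estimate = (crude + Sp − 1) / (Se + Sp − 1). For Sp 98%, Se 90%: (0.0288 − 0.02) / 0.88 = 1.0%. Approximate 95% half-width = 1.96 × √[crude(1 − crude)/n] / (Se + Sp − 1). This treats Se and Sp as known, so a full interval would be wider.

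| n | Sp | True 1% | True 2% |
|---|---|---|---|
| 180 | 98% | −1.8% to 3.8% | −1.2% to 5.2% |
| 180 | 99% | −1.2% to 3.2% | −0.7% to 4.7% |
| 360 | 98% | −1.0% to 3.0% | −0.2% to 4.2% |
| 360 | 99% | −0.6% to 2.6% | 0.1% to 3.9% |

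The correction removes the bias, but three of the four designs would not be expected to exclude zero even at 2%.

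**The case against.** The strongest reply is that the sub-study is descriptive. It sets out to estimate a proportion; it has no test, success criterion or decision. A reader might infer from the hypothesis and the any-detectable rule that past infection will be declared almost whatever the truth. The documents do not support that. Nowhere do they say that one positive, or any count, confirms the hypothesis. A claim that some workers had been infected is wrong only if prevalence is zero or very near it, and these are exposed workers. The chance of a stray positive also depends on an unstated specificity and falls to 16% or 30% at 99.9%. This objection stands, and Step 2 shows only how little a few positives prove.

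Nor do the documents say that baseline prevalence is low, so bias in one direction cannot be presumed. That also stands.

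For seroconversion, the word itself, and the hypothesis's reference to antibodies developing during the study, already imply change from Day 1. That largely stands; the definition needs only to be made explicit.

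The safeguards in the text do not answer the main point. Kit validation is conditional on kits becoming available, and no result feeds the endpoint. Every serum is paired with a swab PCR, but the Introduction says PCR confirms acute infection, so it cannot verify an IgG-only reading. The general caution about validation supports the concern.

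**Conclusion.** The concern holds as a question of bias in estimation. The crude proportion with detectable IgG is not an unbiased estimate of past infection, and neither document provides for a correction. Under the assumed sensitivity of 90% and true prevalence of 1%, it is nearly three times too high at specificity 98%, nearly twice too high at 99%, and about right at 99.9%. Above the break-even prevalence it is too low. All four quantities behind these sizes (sensitivity, specificity, prevalence, uptake) are assumptions.

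Severity is minor. The sub-study is optional and separately consented, and serology enters none of the trial's efficacy endpoints or analyses. It still merits a change, because the individual label goes further than the assay can support and a better estimate is cheap.

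**What to change.** In Protocol 9.8.17, and in the SAP if the sub-study is to be analysed there:

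1. Fix the positivity cut-off before any study sample is tested. Record the assay's sensitivity and specificity with their uncertainty, from its validation sera (known positive and known negative) or from a kit's stated figures.
2. Report the Rogan-Gladen corrected baseline prevalence beside the crude proportion, with a 95% interval that includes the uncertainty in sensitivity and specificity.
3. Conclude that past infection in the cohort is shown only if the lower limit of that interval is above zero.
4. Reword the IgG-only label as *IgG reactive; past infection possible*.
5. State that seroconversion counts only workers who were non-reactive at Day 1.

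This needs no extra participants, visits or draws. It does need validation sera or a kit with published performance, which the protocol does not yet guarantee. The statistical price is a wider interval and limited ability to exclude zero when prevalence is 1% to 2%. As an illustration, a one-sided 5% Fisher comparison of 180 workers with an assumed panel of 200 known-negative sera, at sensitivity 90% and specificity 97% to 99%, would detect a true prevalence of 1% only 8% to 10% of the time and 2% only 16% to 25% of the time. That is a different rule from item 3, but it shows how much uncertainty in specificity costs. The limitation should be reported with the result.

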10. STUDY DRUG MATERIALS AND MANAGEMENT

10.1. Study Drug

Hydroxychloroquine tablets will be used in this study.

10.2. Study Drug Packaging and Labeling

The study drug will be supplied in high-density polyethylene (HDPE) bottles. Each bottle will contain a desiccant insert that must not be ingested. Labeling on each kit bottle will contain at minimum the following information:

- Medication ID number;
- Protocol BSWRI-001;
- Caution Statement: Keep out of sight and reach of children;
- Control or lot number
- Store at 20° – 25°C (68° – 77°F), short term excursions allowed to 15° – 30°C (59° – 86°F);
- BSWRI, Dallas, TX.

A double panel label will be presented on the treatment kit carton containing this and other information as well.

10.3. Study Drug Storage

The stability of the drug product has been and is currently being evaluated in ongoing studies.

Investigative sites must store the investigational product in a secure location with room temperature conditions of 20° - 25°C (68° - 77°F), with brief excursions allowed to 15° – 30°C (59° – 86°F).

10.4. Study Drug Administration

Please refer to [Section 9.8.14](#) for details on study drug administration. Clear instructions will be provided to the subject regarding the number and type of capsules to be ingested at each study drug administration time point listed in [Table 3](#). Subjects must be instructed to continue taking study drug twice on day 1 (two 200 mg twice a day) and once weekly (two 200 mg) after that for a total of 7 weeks unless: (1) subject has been otherwise instructed by the investigator or (2) the subject has been formally discontinued from the study.

10.5. Study Drug Accountability

The investigator, or designee, will maintain a record of all study drug received, dispensed, and returned to the Sponsors' designee. No study drug shall be destroyed by the clinical site unless directed in writing to do so by the Sponsor's quality assurance department. Study drug bottles and any unused capsules should be returned to the study staff for eventual disposition by the Sponsor. The number of capsules returned at each visit will be recorded for each bottle in the kit.

10.6. Study Drug Handling and Disposal

At the conclusion of the study or in an instance of planned study drug replacement, the Sponsor or its designee will direct the site regarding the final disposition of study drug.

11. SAFETY ASSESSMENTS

11.1. Safety Parameters

To avoid inter-observer variability, every effort should be made to ensure that the same individual who made the initial baseline determinations completes all safety assessments. Safety parameters include vital sign measurements, adverse events and serious adverse events.

11.2. Adverse and Serious Adverse Events

11.2.1. Definition of Adverse Events

11.2.1.1. Adverse Event

An adverse event (AE) is defined as any untoward medical occurrence in a subject regardless of its causal relationship to study drug. An AE can be any unfavorable and unintended sign (including any clinically significant abnormal laboratory test result), symptom, or disease temporally associated with the use of the study drug, whether or not it is considered to be study-drug related. Included in this definition are any newly-occurring events or previous condition that has increased in severity or frequency since the administration of study drug.

All AEs that are observed or reported by the subject during the study (from time of administration of the first dose at the Day 1 visit until the final visit indicated in [Table 3](#) must be reported, regardless of their relationship to study drug or their clinical significance.

11.2.1.2. Serious Adverse Event

A serious adverse event (SAE) is any AE occurring at any dose and regardless of causality that:

- Results in death;
- Is life-threatening;
- Requires inpatient hospitalization or prolongation of existing hospitalization;
- Results in persistent or significant incapacity or substantial disruption of the ability to conduct normal life functions;
- Is a congenital anomaly or birth defect in an offspring of a subject taking study drug;
- Is an important medical event.

The term "life-threatening" refers to an event in which the subject was at immediate risk of death at the time of the event. It does not refer to an event that hypothetically might have caused death if it were more severe.

Important medical events are those that may not meet any of the criteria defined above; however, they may be considered serious when, based upon appropriate medical judgment, they may jeopardize the subject and may require medical or surgical intervention to prevent one of the other outcomes listed in the SAE definition.

Pregnancy is not considered an AE; however, information will be collected for any pregnancies that occur during the study (from the time of the first dose of study drug until the final visit

indicated in [Table 3](#), as appropriate). Certain pregnancy outcomes will require submission as an SAE (See [Section 9.6](#)).

The investigator is responsible for reporting to BSWRI or designee all AEs and SAEs that are observed or reported by the subject during the study (from the time of administration of the first dose of study drug until the final visit indicated in [Table 3](#), as appropriate), regardless of their relationship to study drug or their clinical significance.

The Sponsor, or the Contract Research Organization (CRO) on the behalf of the Sponsor, must be notified immediately regarding the occurrence of any SAE that occurs after the subject is enrolled and throughout the study, regardless of study drug administration, including SAEs resulting from protocol-associated procedures, as defined in relevant legislation. The procedures for reporting all SAEs, regardless of causal relationship, are as follows:

- Record the SAE on the AE eCRF and complete the “Serious Adverse Event Report” form within the electronic database.
- In the event the electronic database is not functional, a paper SAE form will be available for the reporting of SAEs.

The Sponsor may request additional information from the investigator to ensure the timely completion of accurate safety reports.

All SAEs reported or observed during the study must be followed to resolution or until the investigator deems the event to be chronic or the subject to be stable. BSWRI or designee may contact the investigator to obtain additional information on any SAE which has not resolved at the time the subject completes the study.

